| 
CONCOMMITANT MEDICATIONS
 | 
Allowed: Patients can receive any other conservative treatments (e.g., oral medications, physical or other therapy, acupuncture, etc., except other injection treatments) and current treatments will be documented during each patient encounter.
 
Prohibited: Since Synvisc is an elastoviscous fluid device injected directly into the knee joint, it does not interfere with any medicine that your physician recommends, including pain relievers and anti-inflammatory drugs.
 |
| 
EFFICACY EVALUATIONS
 | 
Efficacy will be measured and evaluated using data from the following assessments: KOOS, Lysholm, SF-12, WOMAC, and Accelerometer™.
 |

| | |
|--|---|
| PRIMARY ENDPOINT | 
The primary endpoint for the study will be analyzed using a responder analysis. The proportion of responders following injection within the 6 months following the baseline injection will be calculated based on Worst Knee Pain scores ≤ 3 on a 0-10 pain scale, which is a threshold consistent with other similar studies (Tubach 2005, Bellamy 2010). The primary endpoint is defined as non-inferiority of the proportion of responders in our study relative to an external criterion for the responder proportion (Bellamy 2010).
 |
| SECONDARY ENDPOINTS | 
Survival analysis statistics will be performed to assess duration of benefit from the hylan G-F 20 injections over time. A specific timeframe of interest will be the initial 6 months of treatment following the second and any subsequent hylan G-F 20 injection. Changes from baseline to three months post-treatment in activity levels (using objective activity measures utilizing accelerometer and Physical Activity Enjoyment Scale) and quality of life scores (WOMAC, SF-12) will be determined. We will examine the time courses of longitudinal measures of pain score, activity level, and quality of life over the entire three-year span of the study.
 |

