| 
STATISTICS Secondary Endpoints
 | 
For subsequent injections, duration of response over time and median duration of response will be estimated using survival analysis techniques. Inference for activity levels and quality of life will focus on changes from baseline to 3 months. We will examine the time course for the longitudinal data on pain score, activity level, and quality of life measures across the three years of the study using mixed effects models.
 |
| 
Rationale for Number of Subjects
 | 
Power Calculation
 
Bellamy demonstrated in his paper from 2007 (table 3) that a BLISS response at any time during the study was achieved in 70% receiving appropriate care and Hylan G-F 20 and only in 38% of patients receiving appropriate care ($P < 0.0001$). A power calculation using a one-sample comparison of proportion with hypothesized value sample size was performed to determine non-inferiority to the 70% results quoted by Bellamy. Power calculations were measured using STATA's SAMPSI calculator. If we postulate a 20% non-inferiority limit (i.e. that at least 50% of patients receiving G-F 20 will achieve a BLISS response), the sample size required to have 90% power and
 |

| | |
|------------------------------------|--|
| | 
$\alpha=0.025$ to show non-inferiority at 50% would be 70. For a 10% non-inferiority limit with 90% power and $\alpha=0.025$, the required sample size is 274, and for 15% non-inferiority limit with 90% power and $\alpha=0.025$, it is 124 patients. These numbers do not allow for dropouts, therefore, we intend to recruit 150 subjects to account for dropout.
 
Conservatively assuming a 20% rate of drop-out, the resulting sample size of $n=120$ has better than 90% power (one sided test with $\alpha=0.025$) to show non-inferiority assuming the true responder rate is 65% (i.e. not quite as high as the 70% external reference).
 |
| 
DATA MANAGEMENT PLAN
 | 
Data management and analysis for the study will be performed by the Biostatistics Consulting Unit (BCU) of UCSF’s Clinical and Translational Science Institute (CTSI). Data will be stored on a HIPAA-compliant server. The server room has state-of-the-art environmental controls and security features and is protected by a firewall and anti-virus software.
 |

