2.2 Secondary Objectives

There are two secondary objectives to this study:

Specific Aim 3: To identify the effects of treatment with hylan G-F 20 on activity levels (using objective activity measures utilizing accelerometer and Physical Activity Enjoyment Scale (PACES)) and quality of life scores (WOMAC, SF-12) comparing baseline to treatment at 3 months.

Specific Aim 4: is to understand the natural history of conservative treatment on this cohort of patients over a 3 year period.

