4 CRITERIA FOR EVALUATION

4.1 Primary Efficacy Endpoint

Co-Primary endpoints

- o Proportion of subjects reporting being in PASS during at least one Study Contact Point during entire 36 month study period
- o Proportion of Study Contact Points that each subject reports being in PASS during entire 36 month study period

Secondary endpoints

- o Change in scores over 36 months for:

- o Worst Knee Pain
- o Five KOOS domains
- o SF-12
- o 12-minute walk test
- o 3-day accelerometer test

The primary endpoint for the study will be analyzed using a responder analysis. The proportion of responders following injection within the 6 months following the baseline injection will be calculated based on Worst Knee Pain scores. A specific timeframe of interest will be the initial 6 months of treatment following the second and any subsequent hylan G-F 20 injection.

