13 STATISTICAL METHODS AND CONSIDERATIONS

Prior to the analysis of the final study data, a detailed Statistical Analysis Plan (SAP) will be written describing all analyses that will be performed. The SAP will contain any modifications to the analysis plan described below.

Data Sets Analyzed

The primary endpoint is based on a responder analysis. Response is defined as maintaining a Worst Knee Pain score ≤ 3 on a 0-10 pain scale throughout the 6 months following the baseline injection. Trial success will be based on a non-inferiority test (with 20% non-inferiority threshold) of this response rate in comparison to an external criterion of 70% (Bellamy 2010). Secondary endpoints include determining the duration of response after subsequent injection, determining the effects of treatment on activity levels and quality of life, and describing the three-year time course of each of the study endpoints. The sample size will be $n=150$ subjects followed for up to 3 years after baseline injection. The power to conclude non-inferiority for a true response rate of 65% is better than 92%.

Demographic and Baseline Characteristics

The following demographic variables at screening will be summarized by: race, gender, age, height and weight.

Analysis of Primary Endpoint

The primary endpoint for the study will be analyzed using a responder analysis. The proportion of responders following injection within the 6 months following the baseline injection will be calculated based on Worst Knee Pain scores ≤ 3 on a 0-10 pain scale, which is a threshold consistent with other similar studies (Tubach 2005, Bellamy 2010). The primary endpoint is defined as non-inferiority (with 20% non-inferiority threshold) of the proportion of responders in our study relative to an external criterion of 70% for the responder proportion (Bellamy 2010).

Primary Statistical Analysis: Define the true probability of a subject being a responder as π and the non-inferiority threshold $\delta_{NI} = 0.20$. We require the test of

$$H_0: \pi < 0.70 - \delta_{NI} = 0.50$$

vs. the alternative

$$H_1: \pi \geq 0.70 - \delta_{NI} = 0.50.$$

Non-inferiority will be accepted if the null hypothesis can be rejected with a 2.5% one-sided type I error. To test this hypothesis, we will use the Wilson-Agresti method for a single binomial proportion. Non inferiority will be accepted if the 95% Wilson-Agresti (REF BROWN ET AL 2001) interval for the proportion of responders excludes the null rate of 0.50.

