Missing Data:For the analysis of the percentages of positive responders, patients who discontinue the study prior to the Week 26 assessment due to either target knee-related AEs or due to lack of efficacy will be classified as non-responders in the efficacy analysis. Patients who discontinue the study for other reasons will have the responder status imputed using the last observation carried forward (LOCF) method.

Operating Characteristics

The following table shows the power to accept non-inferiority for two assumptions on sample size (n=150 and a smaller sample size reflecting potential dropout of n=120):

| True Responder Rate (□. | Sample Size n=150 | Sample Size n=120 |
|----------------------------|----------------------|----------------------|
| 0.60 | 72% | 61% |
| 0.65 | 97% | 92% |
| 0.70 | >99% | >99% |
| 0.75 | >99% | >99% |

Table 1. Power to conclude non-inferiority for variety of true responder rates and two values for sample size.

Thus, even after conservatively accounting for subject dropout, we will be well-powered to conclude non-inferiority if the true responder rate is at least 65%.

Secondary Outcomes:

- **Duration of response to subsequent injections:** Though symptoms can be improved for periods up to 6 months, pain symptoms can recur in which case patients will receive a subsequent injection. The duration of these repeated treatments of hylan G-F 20 will be studied.

- **Effect of treatment on activity levels and quality of life:** The effects of treatment with hylan G-F 20 on activity levels (using objective activity measures utilizing accelerometer

and Physical Activity Enjoyment Scale) and quality of life scores (WOMAC, SF-12) comparing baseline to treatment at 3 months.

- **Three year follow up:** Patients will be followed for up to three years. We will examine the time courses of pain score, activity level, and quality of life over the entire three year span.

Analysis of Secondary Endpoints

Secondary Analyses: Secondary endpoints will be analyzed using confidence intervals as no specific hypothesis tests are being conducted.

The following secondary analyses will be conducted:

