- **Duration of response:** Using Kaplan-Meier survival analysis techniques, we will estimate the probability of duration of response over time curve (survival curve) and its confidence limits and also the median duration time and confidence interval. Duration of response analyses will be conducted for the initial injection and also in the subset of patients that receive a follow-up injection.

- **Activity levels and quality of life:** We will estimate the average change and corresponding confidence limits from baseline to 3 months in each of the activity level measures (accelerometer test, walk test, Physical Activity Enjoyment Scale) and the quality of life measures (WOMAC, SF-12). The confidence intervals will be constructed using one sample t-distributions; in the event of strongly skewed measures, we will either use bootstrapping or transformation to construct more accurate intervals. The average change and the endpoints of the confidence intervals can be referenced to external clinically important improvements for comparison.

- **Long term outcome:** We will examine the time course for the pain score, activity level, and quality of life measures across the three years of the study. Estimates and confidence intervals will be derived using mixed effects linear models. Specifically, for each longitudinal outcome measure, we will model it as a function of the (categorical) time point. Intrasubject correlation will be accommodated by either a compound symmetry, autoregressive, or general covariance structure depending on best fit according to BIC. In the event of very non-normally distributed outcomes, we will employ normalizing transformations prior to the analysis. These analyses will be conducted using the Mixed procedure in SAS.

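### Section 13 estimates change from baseline to 3 months in five measures, but three have no value scheduled between screening and month 6, PACES has no visible schedule, and WOMAC at week 12 is described inconsistently

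*Combined protocol and SAP*

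**What the plan says.** The 3-month time point is stated consistently.

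- Section 2.2 frames Aim 3 as "comparing baseline to treatment at 3 months", and the synopsis objectives say the same.
- The synopsis secondary endpoints give "Changes from baseline to three months post-treatment in activity levels".
- The synopsis statistics entry for secondary endpoints says "Inference for activity levels and quality of life will focus on changes from baseline to 3 months".
- Section 13 sets the estimator: "We will estimate the average change and corresponding confidence limits from baseline to 3 months in each of the activity level measures". It names accelerometer, walk test and PACES as activity measures and WOMAC and SF-12 as quality-of-life measures, with one-sample t intervals. A separate item plans mixed models of pain, activity and quality of life over three years.

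The collection side reads differently. Appendix 1 and section 9 place accelerometer, walk test, SF-12 and WOMAC at screening and then at six-monthly visits from month 6. Sections 8.1.7 and 8.1.12 also put the first repeat at month 6. The synopsis efficacy evaluations refer to "data from the following assessments: KOOS, Lysholm, SF-12, WOMAC" and the accelerometer, without PACES.

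Sections 4.1 and 4.2 list secondary endpoints as "Change in scores over 36 months for" Worst Knee Pain, KOOS, SF-12, walk test and accelerometer.

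**The concern.** An analysis time point needs a measurement at or near it. Here the aim, the endpoint and the estimator all point to month 3, while the visit schedule jumps from screening to month 6. If the trial runs as scheduled, the Aim 3 question cannot be answered as written for most of its measures, and a PACES baseline not taken before the injection cannot be recovered. Section 4 does not help a reader settle the endpoint, because it mentions neither the 3-month change nor PACES nor WOMAC. An undefined time point also leaves room to choose one after the data are seen.

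**Working it through.** **Step 1. Reproduce the plan's own time budget.** The synopsis entry on duration of participation gives about 8 clinical hours, 21 accelerometer days and 4.5 hours of remote contact. From the listed visits:

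- Accelerometer: screening plus months 6, 12, 18, 24, 30 and 36 is 7 sessions; 7 × 3 days = 21 days.
- Clinic: 2 h at baseline + 6 × 1 h = 8 h.
- Remote contact: 6 cycles × 3 contacts × 15 min = 270 min = 4.5 h.

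All three figures come out exactly from a schedule with no 3-month visit. One added in-person assessment at month 3 would give 8 × 3 = 24 days and 2 + 7 × 1 = 9 h. The 3-month accelerometer and walk test are therefore unbudgeted, and not just missing from one table.

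**Step 2. Count scheduled values for each measure in section 13.**

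| Measure | Named in Aim 3 | Visit-schedule values between screening and month 6 | Remote contact at week 12 | 3-month change |
|---|---|---|---|---|
| Accelerometer | yes | 0 | not listed | not computable |
| Walk test | no (section 13 only) | 0 | not listed | not computable |
| SF-12 | yes | 0 | not listed | not computable |
| WOMAC | yes | 0 | sections conflict | uncertain |
| PACES | yes | 0, and no baseline entry visible | not listed | no visible source |

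Sources: Appendix 1; sections 8.1.7, 8.1.12 and 9; and for the contacts the synopsis study design and sections 3.1, 7.4.1, 7.7, 8.1.11 and 9. By section 13's list, three of five cannot be computed. By Aim 3's own list it is two of four (accelerometer, SF-12).

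**Step 3. WOMAC at week 12.** One paragraph, repeated in the synopsis study design, 3.1 and 7.4.1, makes WOMAC, Lysholm and Tegner the content of the 6-, 12- and 18-week contacts. Sections 7.7, 8.1.11 and 9 instead list pain, other treatment history and adverse events. Because each version is partly repeated text, counting sections does not settle which governs. If the first does, week 12 is 84 days against about 91 days for 3 months (365.25 / 4), which is close enough to serve.

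**Step 4. Could retreatment supply the value?** No. The earliest retreatment in the synopsis is 4 months.

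**Step 5. What happens at month 6.** The synopsis says that follow-up restarts at Visit 1 after another injection. A subject retreated at 4 months would then have the next Visit 2 at 4 + 6 = 10 months after baseline. Against that, section 3.1 provides a visit 6 months after the first injection, and the missing-data rule in section 13 presupposes a Week 26 assessment. The documents give no retreatment rate, so the number of subjects concerned cannot be stated.

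**Step 6. Month 12 (separate and minor).** Sections 8.1.7 and 8.1.12 leave out month 12; the synopsis, section 9 and Appendix 1 include it. Without it the accelerometer total is 6 × 3 = 18 days, not the stated 21.

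**The case against.** **A later SAP can settle this.** Section 13 does say "The SAP will contain any modifications to the analysis plan described below". That SAP can move the time point. It is to be written before the final analysis, however, and cannot create month-3 measurements.

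**Appendix 1 proves little about week 12.** This stands in part. Appendix 1 has no columns for remote contacts and omits even the Worst Knee Pain contacts in section 9, so it is no evidence against WOMAC at week 12. It does not rescue the others: no description of those contacts mentions SF-12, PACES, accelerometer or walk test.

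**These are only secondary estimates.** Correct: "Secondary endpoints will be analyzed using confidence intervals as no specific hypothesis tests are being conducted". That limits the weight of the point but does not remove it.

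**Moving everything to month 6 changes the question.** This is a fair objection. Section 1 puts benefit at up to 6 months, and section 1.2 reports, for the three-injection product, the greatest relief at 8 to 12 weeks. A month-6 reading comes at the end of that window. The choice should be the sponsor's, with the downside stated.

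Four stronger readings are tempting but not supported:

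- *PACES is never collected.* The case report forms in Appendix II are not shown, so it can only be said that no schedule for it is visible.
- *Section 4 replaces the 3-month endpoint with a rival one.* The synopsis and section 13 plan both a 3-month change and a three-year time course. Section 4 largely matches the second and is incomplete.
- *Retreated subjects will have no month-6 visit.* Section 3.1 and the Week 26 assessment point the other way.
- *The three-year models are untouched.* PACES, if modelled as an activity measure, has no visible data source there either, and the month-12 conflict concerns one of the modelled time points.

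**Conclusion.** The point holds and should be fixed. As scheduled, the 3-month change cannot be computed for three of the five measures in section 13 (accelerometer, walk test, SF-12) and is uncertain for the other two (WOMAC, PACES). For the first three, the earliest post-injection value is at month 6, twice the stated interval. Section 4 omits the 3-month change, PACES and WOMAC. What is lost is the answer to Aim 3 as written; the primary endpoint is not affected.

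The conclusion rests on a comparison of the plan's own sections and on no assumed rate or variance. It depends on the visible text being the full schedule, and the unseen case report forms could change this for PACES in particular.

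**What to change.** 1. **SF-12 and WOMAC:** keep 3 months. Add SF-12 to the existing week-12 email or phone contact, and reconcile the synopsis study design, 3.1 and 7.4.1 with 7.7, 8.1.11 and 9 so that WOMAC is collected there.
2. **Accelerometer and walk test:** change the time point in the synopsis, 2.2 (which names only the accelerometer) and 13 to the scheduled 6-month visit, unless the sponsor chooses to schedule a 3-month collection. State that month 6 is the end of the stated benefit window and that some subjects may have been retreated from month 4. Reconcile the synopsis restart rule with the 6-month visit in 3.1 and the Week 26 assessment in 13, and report how many subjects were retreated before month 6.
3. **PACES:** add it to screening, the chosen follow-up contact and Appendix 1, or delete it from Aim 3 and section 13.
4. **Section 4:** align it with section 13 in measures and time points.
5. **Month 12 (minor):** reconcile 8.1.7 and 8.1.12 with the synopsis, section 9 and Appendix 1. The stated 21 accelerometer days fit only if month 12 is included.

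**Cost:** a wording amendment and one or two short questionnaires at an existing contact, with no new clinic visit. If the sponsor prefers a 3-month in-person assessment, the budget rises to 24 accelerometer days and about 9 clinical hours. Reading activity at month 6 has its own cost: Aim 3 would then have activity at 6 months and quality of life at 3, and the month-6 values would mix retreated and non-retreated subjects or, if the restart rule removes that visit, come from a selected group.

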| | 
enrolled in the cohort will have baseline functional testing performed including a motion gait analysis, 12 minute walk test, and 3-day accelerometer data. Subjects will receive a single 6 mL intra-articular injection of hylan G-F 20 in the target knee at baseline. All ongoing treatments will be monitored at 6-month intervals over the 3-year duration of the study. Patients can receive any other conservative treatments (e.g., oral medications, physical or other therapy, acupuncture, etc., except other injection treatments) and current treatments will be documented during each patient encounter. An initial injection of hylan G-F 20 will be injected in the symptomatic knee using a standard supine lateral approach using a 20-gauge needle. A face-to-face follow up visit will be carried out 6 months after first injection with additional face to face meetings every 6 months thereafter unless the subject requires an additional injection of hylan G-F 20. Hylan G-F 20 treatments can be administered up to three times each year during the study duration. After each injection, follow up measures will be carried out using secure e-mail or phone contact at 6 weeks, 12 weeks, 18 weeks after each in-office evaluation or injection. Follow up will consist of WOMAC, Lysholm score, and Tegner score. Patients may return for retreatment of hylan G-F 20 if symptoms recur after at least 4 months following their previous injection and they meet the inclusion criteria for pain levels on the following WOMAC questions A1 (How much pain have you had walking on a flat surface?), C8 (How much difficulty have you had going down the stairs?), C9 (How much difficulty have you had when going up the stairs?), C10 (How much difficulty have you had when getting up from a sitting position?) and/or C23 (How much difficulty have you had while doing heavy household chores?). Inclusion criteria for pain level is defined by selecting moderate, severe, or extreme on all questions A1, C8, C9, C10 and/or C23. Those subjects who select mild or no pain levels on any of A1, C8, C9, C10 and/or C23, will not meet the criteria for WOMAC pain level and retreatment. Patients requiring three injections of hylan G-F 20 in 4 months or less will be allowed to exit the cohort after their six-month follow up following the third injection. Otherwise, patients will be followed until they reach the 3-year follow up, or drop out for other injection treatments or surgical treatment. Therefore, patients would potentially be able to receive up to 9 injections during the 3-year study.
 |

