| TEST PRODUCT, DOSE, AND ROUTE OF ADMINISTRATION | 
Synvisc G-F 20 will be injected in the symptomatic knee using a standard supine lateral approach using a 20-gauge needle. Patients will be treated at baseline and followed out to three years. Patients may return for retreatment as early as 4 months post their prior injection if they meet the retreatment criteria pain levels for Worst Knee Pain. If the subjects need another injection, the follow-up cycle will restart at Visit 1 and the subject will be seen every 6 months and followed-up for 3 years.
 |
| CONTROL PRODUCT, DOSE AND ROUTE OF ADMINISTRATION | N/A |

| | |
|---|--|
| 
DURATION OF SUBJECT PARTICIPATION AND DURATION OF STUDY
 | 
Patients may return for retreatment as early as 4 months post their prior injection if they meet the retreatment criteria pain levels for Worst Knee Pain. If the subjects need another injection, the follow-up cycle will restart at Visit 1 and the subject will be seen every 6 months and followed-up for 3 years.
 
Approximate Time Requirements:
 
 • Baseline Screening: Informed Consent, Physical exam, patient questionnaire, injection, X-ray, walk test (Approx. 2 hours) and accelerometer test (3 days) • 6 months after injection: Physical exam, patient questionnaire, walk test (Approx. 1 hr) and accelerometer test (3 days) • 12 months after injection: Physical exam, patient questionnaire, walk test (Approx. 1 hr) and accelerometer test (3 days) • 18 months after injection: Physical exam, patient questionnaire, walk test (Approx. 1 hr) and accelerometer test (3 days) • 24 months after injection: Physical exam, patient questionnaire, walk test (Approx. 1 hr) and accelerometer test (3 days) • 30 months after injection: Physical exam, patient questionnaire, walk test (Approx. 1 hr) and accelerometer test (3 days) • 36 months after injection: Physical exam, patient questionnaire, walk test (Approx. 1 hr) and accelerometer test (3 days) • 15 min email or phone contact at 6, 12, and 18 weeks post each injection and clinic visit (total 4.5 hrs) 
Total time for the study will be approximately 8 clinical hours over 3 years, 21 days for the accelerometer test and 4.5 hrs of email/phone contact.
 |

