duration of the study. Patients can receive any other conservative treatments (e.g., oral medications, physical or other therapy, acupuncture, etc., except other injection treatments) and current treatments will be documented during each patient encounter. An initial injection of hylan G-F 20 will be injected in the symptomatic knee using a standard supine lateral approach using a 20 gauge needle. A face to face follow up visit will be carried out 6 months after first injection with additional face to face meetings every 6 months thereafter unless the subject requires an additional injection of hylan G-F 20. Hylan G-F 20 treatments can be administered up to three times each year during the study duration. After each injection, follow up measures will be carried out using secure e-mail or phone contact at 6 weeks, 12 weeks, 18 weeks after each in-office evaluation or injection. Follow up will consist of WOMAC, Lysholm score, and Tegner score. . Patients may return for retreatment of hylan G-F 20 if symptoms recur after at least 4 months following their previous injection and they meet the inclusion criteria for pain levels on the following WOMAC questions A1 (How much pain have you had walking on a flat surface?), C8 (How much difficulty have you had going down the stairs?), C9 (How much difficulty have you had when going up the stairs?), C10 (How much difficulty have you had when getting up from a sitting position?) and/or C23 (How much difficulty have you had while doing heavy household chores?). Inclusion criteria for pain level is defined by selecting moderate, severe, or extreme on all questions A1, C8, C9, C10 and/or C23. Those subjects who select mild or no pain levels on any of A1, C8, C9, C10 and/or C23, will not meet the criteria for WOMAC pain level and retreatment. Patients requiring three injections of hylan G-F 20 in 4 months or less will be allowed to exit the cohort after their six-month follow up following the third injection. Otherwise, patients will be followed until they reach the 3 year follow up, or drop out for other injection treatments or surgical treatment. Therefore, patients would potentially be able to receive up to 9 injections during the 3 year study.

Total time for the study will be approximately 8 clinical hours over 3 years, 21 days for the accelerometer test and 4.5 hrs of email/phone contact.

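### The documents give two visit clocks for re-injected subjects; under the restart rule the clinic-only outcomes go unmeasured at the 6-month points from baseline that the three-year analysis needs

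*Combined protocol and SAP*

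**What the plan says.** **Restarting clock.** The synopsis, under Test Product and again under Duration of Subject Participation, says that after another injection "the follow-up cycle will restart at Visit 1 and the subject will be seen every 6 months and followed-up for 3 years". Section 3.1, repeated in substance in the synopsis Study Design and in Section 7.4.1, provides for a 6-month visit with "additional face to face meetings every 6 months thereafter unless the subject requires an additional injection of hylan G-F 20".

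**Single clock.** Section 3.1 also says that, apart from early exits, "patients will be followed until they reach the 3 year follow up". Section 13, Data Sets Analyzed, has "subjects followed for up to 3 years after baseline injection". The secondary outcomes in Section 13 refer to the whole three-year span.

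**Re-injection.** It is allowed "if symptoms recur after at least 4 months following their previous injection", and "Hylan G-F 20 treatments can be administered up to three times each year during the study duration". The synopsis concludes that "patients would potentially be able to receive up to 9 injections during the 3-year study".

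**Analysis.** For the long-term outcomes, Section 13 fits a linear mixed model to each measure separately: "we will model it as a function of the (categorical) time point". It does not say whether time runs from baseline or from the latest injection. Section 9 labels visits by months after injection without saying which injection.

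**Measurements.** Appendix 1 schedules KOOS, SF-12, WOMAC, Worst Knee Pain, the walk test and accelerometry at screening and at Visits 2 to 7, and none of them at Visit 1. Between visits, contacts at 6, 12 and 18 weeks collect Worst Knee Pain (Section 9) and WOMAC, Lysholm and Tegner (Section 3.1).

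**The concern.** Re-injection can come at 4 months, before the first 6-month visit. Under the restart rule it sends the subject back to Visit 1, where no outcome is scheduled, so the injection visit does not replace the assessment it displaces. KOOS, SF-12, the walk test and accelerometry have no other scheduled collection.

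These four are among the five Section 4.2 endpoints, all defined as change over 36 months, and they inform Aim 4 on the course of the whole cohort. The visits lost belong to the subjects whose symptoms came back. A later SAP can define the time variable, but it cannot supply measurements that were never taken.

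**Working it through.** **1. The plan's own figures.**
- Injections every 4 months within 36 months fall at 0, 4, 8, 12, 16, 20, 24, 28 and 32. That is 9, as stated.
- Clinic time: 2 h + 6 × 1 h = 8 h. Accelerometer: 7 × 3 days = 21 days. Contacts: 6 × 3 × 15 min = 4.5 h. All three match the synopsis.

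The time budget therefore describes one uninterrupted calendar of six post-baseline visits, although the restart rule stands in the same synopsis entry.

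**2. Rule applied.** After an injection at month *t*, visits fall at *t* + 6, *t* + 12, …, *t* + 36 and carry the labels Visit 2 to Visit 7. A visit is dropped if another injection comes first. The documents give no re-injection frequency, so the patterns below are assumptions within what the plan allows.

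**3. Follow-up capped at 36 months from baseline.**

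| Injections at month | Clinic visits at month | Labels |
|---|---|---|
| 0 only | 6, 12, 18, 24, 30, 36 | Visits 2–7 |
| 0 and 5 | 11, 17, 23, 29, 35 | Visits 2–6 |
| 0 and 10 | 6, 16, 22, 28, 34 | Visits 2, 2, 3, 4, 5 |
| every 8 (0–32) | 6, 14, 22, 30 | all Visit 2 |
| every 6 (0–30) | 6, 12, 18, 24, 30, 36 | all Visit 2, if each visit precedes the same-day injection |
| every 5 (0–35) | none | – |
| every 4 (0–32) | none | – |

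Visit 7 needs *t* + 36 ≤ 36, so *t* = 0: only subjects never re-injected reach it.

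**4. Three years counted from the last injection instead.** The 4-monthly subject has a last injection at month 32 and visits at 38, 44, 50, 56, 62 and 68. Six visits are held, all outside the three-year span to be estimated.

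**5. What is still collected.** Four months is 4 × 365.25 / 12 / 7 = 17.4 weeks, so a 4-monthly subject can be re-injected before the 18-week contact. The 6- and 12-week contacts remain: 9 × 2 = 18 contacts with Worst Knee Pain and, per Section 3.1, WOMAC. KOOS, SF-12, walk test and accelerometry have only the screening value within 36 months.

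**6. Direction.** Re-injection requires recurrent symptoms, so the missing visits depend on the course of the disease. Each outcome has its own model in time alone, so remotely recorded pain does not inform the missing SF-12 or walk test. Late estimates would rest mainly on subjects who needed few re-injections.

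**The case against.** The strongest reply is that the statistics section already points to time since baseline. Section 13 follows subjects for three years after the baseline injection, Section 3.1 monitors treatments at 6-month intervals over the study, and the time budget fits a fixed calendar. A SAP is promised before final analysis and can set the origin and windows. This stands in part. A reader might infer that the model's time factor is the visit label, so that month 6 in the results would mix true months 6 and 10 to 36. Section 13 never says so; that mixing is one possible reading.

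A reader might also infer that frequently re-injected subjects contribute no data. That is not supported either: they give baseline values and remote Worst Knee Pain and WOMAC, which can be placed on months since baseline. The gap is confined to the clinic-only measures.

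The scenarios with no visits need every interval to be shorter than 6 months throughout, and nothing in the documents says how common that is. Section 3.1 also lets some frequently injected subjects leave early. As worded (three injections in 4 months or less), that provision sits badly with the 4-month minimum interval and needs reconciling too. Exit is permitted, not required, so the scenarios remain possible.

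Finally, this is a secondary analysis by confidence intervals without hypothesis tests, and the primary responder test does not use it. That limits the weight of the point. It does not remove the conflict between the two clocks, or the fact that visits not held cannot be recovered.

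**Conclusion.** The point holds as a conflict over the visit clock, with an undefined time origin in the three-year model. It should be corrected during conduct, because part of the damage is uncollected data.

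If the restart rule is followed, clinic-only outcomes are not measured at 6-month points from baseline in re-injected subjects. With a 36-month cap, the number of clinic visits runs from six (never re-injected) down to four (every 8 months) and none (every 4 or 5 months). With three years from the last injection, the 4-monthly subject's visits fall at months 38 to 68.

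The loss is informative, and the three-year course of KOOS, SF-12, walk test and accelerometry would lean towards subjects needing few re-injections. The size of that bias cannot be computed, because the documents give no re-injection rates. The documents do not support extending this to a complete absence of data, to certain mixing of times in the model, or to bias in the primary test through this model.

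**What to change.** 1. Reconcile the synopsis (Study Design, Test Product, Duration of Subject Participation), Sections 3.1, 7.4.1, 9 and 13, and Appendix 1 on one visit clock. This concerns when outcomes are measured; it needs no change to when subjects may be re-injected.
2. Keep the 6-monthly assessments (questionnaires, walk test, accelerometry) at months 6 to 36 after the baseline injection for every subject, re-injected or not. Remote questionnaires alone are not enough, since they cannot replace the walk test or accelerometry.
3. In the SAP, define the model's time point as months since the baseline injection, with visit windows.
4. Do not add number of injections or time since last injection as ordinary covariates in the main model. Both follow from earlier pain, and adjusting for them changes the estimand from the cohort's course under as-needed retreatment. At most, use them in an analysis labelled exploratory.

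The cost is protocol and SAP wording, and some re-injected subjects will attend a 6-month visit close to an injection visit. Six post-baseline visits per completer are already in the synopsis time budget.
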